# 6.3.1 *Risk assessment with regards to the COVID-19 pandemic*

Current recommendations from the authorities will be considered on a day-to-day basis and a continuous risk evaluation will be made to assess how the COVID-19 pandemic is affecting the study conduct and the safety of the study subjects.

Any identified risks in terms of subject safety, trial performance and data quality/integrity will be documented in a risk log as part of the Sponsor's trial master file (TMF).

Clinical Trial Protocol VP-C106-101 Final v4.0

The recommendations from the EMA [37, 38] as well as the Swedish Medical Products Agency (MPA) [39] regarding the conduct and management of clinical trials during the COVID-19 pandemic will be taken into consideration.

# 7 TRIAL OBJECTIVES AND ENDPOINTS

# 7.1 Objectives and endpoints

The objectives, endpoints and assessments are summarised in Table 7.1-1. The exploratory endpoints (MIST, urine metabolites and endothelial function) may be reported separately from the clinical trial report (CTR). Cardiodynamic ECG data will be stored for potential future evaluation and will thus not be included in the CTR.

Endpoint	Assessment(s)		
Treatment emergent AEs and SAEs	AE reporting and questioning (Section 11.3.1)		
Clinically significant changes in 12-lead electrocardiograms (ECGs), vital signs, laboratory safety variables (haematology, coagulation, clinical chemistry and urine analysis), and physical examinations.	12-lead ECG (Section 11.3.2), Vital signs (Section 11.3.4), Blood sampling for clinical chemistry and haematology, urine sampling for urinalysis (Section 11.3.5), Physical examination (Section 11.3.6).		

 
Part A
 
AUC from time 0 to infinity (AUCinf) and AUC from time 0 to the time of the last quantifiable concentration (AUClast,).
 
Plasma half-life associated with the terminal elimination phase (T1/2(z)), Cmax and time to Cmax (Tmax).
 
Total clearance of the drug from plasma following oral administration (CL/F) and apparent volume of distribution associated with the terminal elimination phase (Vz/F).
 
Dose proportionality after a single oral dose based on AUCinf and Cmax.
 
% of dose excreted unchanged in urine.
 
Renal clearance.
 
Part B
 
PK parameters after the first dose: 
 
AUC over the dosing interval (AUCtau), AUCinf, T1/2(z), Cmax, Tmax, CL/F, Vz/F.
 
 
 
PK parameters after the last dose: 
 
AUC at steady state (AUCtau), T1/2(z), Cmax, Tmax, CL/F, Vz/F.
 
 
 
	Pharmacokinetic sampling and analysis (Section 11.4.1 and Section 11.4.2).		
	
 
Treatment emergent AEs and SAEs
 
Clinically significant changes in 12-lead electrocardiograms (ECGs), vital signs, laboratory safety variables (haematology, coagulation, clinical chemistry and urine analysis), and physical examinations.
 
Part A
 
AUC from time 0 to infinity (AUCinf) and AUC from time 0 to the time of the last quantifiable concentration (AUClast).
 
Plasma half-life associated with the terminal elimination phase (T½(Z)), Cmax and time to Cmax (Tmax).
 
Total clearance of the drug from plasma following oral administration (CL/F) and apparent volume of distribution associated with the terminal elimination phase (Vz/F).
 
Dose proportionality after a single oral dose based on AUCinf and Cmax.
 
% of dose excreted unchanged in urine.
 
Renal clearance.
 
Part B
 
PK parameters after the first dose: 
 
AUC over the dosing interval (AUCtau), AUCinf, T½(2), Cmax, Tmax, CL/F, Vz/F.
 
PK parameters after the last dose:
 
AUC ot steady state (AUCtau), T½(z), Cmax,
 
 
 
		

Table 7.1-1 Objectives and endpoints

To evaluate the effect of a high fat meal on the single oral dose PK of C106 in healthy subjects (Part A). Exploratory	
 
Dose proportionality (based on AUCtau and Cmax) and accumulation ratios (based on AUCtau and Cmax).
 
Observed concentration at the end of a dosing interval, immediately before next administration (Ctrough).
 
PK parameters as for Part A.
 
Relative bioavailability of C106 in fasted versus fed conditions.
 
			
To evaluate the	Metabolite In Safety Testing (MIST) analysis of	MIST (Section 11.5.1).		
metabolite profile of C106 in plasma of healthy subjects at steady state (Part B).	the metabolite profile in plasma in comparison with the metabolite profile in plasma from non- clinical safety studies.	NIIST (Section 11.5.1).		
To estimate the excreted C106 and its metabolites and the metabolite profile of C106 in urine of healthy subjects at steady state (Part B).	Profile of excreted metabolites in the urine.	Urine sampling and analysis (Section 11.5.2).		
To collect and store ECG data for potential future evaluation of the effect of C106 on ECG parameters, including concentration-QTc analysis using Expert Precision QT (EPQT) assessment (Part A).	Cardiodynamic ECG parameters.	EPQT assessment (Section 11.5.3).		
To evaluate the pharmacodynamicChange from baseline in reactive hyperemia index (RHI) and augmentation index (AI) scores at Day 7 as measured by EndoPAT.(PD) effect of C106 on endothelial function in healthy subjects at steady state (Part B, cohort B4).Day 7 as measured by EndoPAT.		EndoPAT assessment (Section 11.5.4).		

# 8 TRIAL DESIGN

# 8.1 Overall trial design and schedule of events

This is a FIH, double-blind, placebo-controlled, within-group randomised, trial designed to evaluate the safety, tolerability and PK of single and multiple ascending oral doses of C106 in healthy females of non-childbearing potential and healthy males.

[figure not shown]
The trial will be conducted in 2 parts:

[figure not shown]
**Part A**, SAD including a food interaction cohort: safety, tolerability and PK in healthy males and healthy females of non-childbearing potential receiving single ascending doses of C106, see Section 8.1.1.

**Part B**, MAD: safety, tolerability and PK in healthy males and healthy females of nonchildbearing potential receiving twice daily multiple ascending doses of C106 for 8 days, see Section 8.1.2.

Subjects included in the SAD part of the present study will not be included in the MAD part (regardless of whether 3 months have passed since the SAD participation).

[figure not shown]
An overview of the planned cohorts and the trial design is shown in Figure 8.1-1 and Figure 8.1-2.

The actual doses given in Part A for cohorts 1 to 4 were 5, 30, 60 and 180 mg, corresponding to dose increment of 6, 2 and 3 times the previous dose. For cohort 5 and 6, the planned doses are 240 mg and 300 mg, corresponding to dose increments of 1.3 and 1.25 times the previous dose, respectively. The dose given in cohort 6 may be adjusted as recommended by the iSRC following evaluation of emerging safety, tolerability, and PK data in cohort 5. Cohorts A7, A8 and B5 are optional. The maximum oral dose in Part A and the maximum oral daily dose in Part B will not exceed 480 mg C106 (including the optional cohorts). The fed cohort is planned to be cohort A4. The first cohort in Part B (MAD) may be dosed after safety evaluation of the SAD cohort A3 if recommended by the iSRC. Each dose level in Part B will be selected such that the predicted maximum exposure will not exceed the maximum exposure (based on AUC and Cmax) in previously evaluated SAD cohorts. Day 8: only morning dose (*i.e.*, in total 15 doses in Part B). The dosing frequency in Part B is planned to be BID but may be changed to QD if recommended by the iSRC.

### Figure 8.1-2 Overview of the trial design

# 8.1.1 Single Ascending Dose (SAD) part of the trial

In Part A, single, oral doses of C106 will be administered in 6 sequential dose cohorts, each of 8 subjects. Within each cohort, subjects will be randomised to receive either C106 (n=6) or placebo (n=2) in the fasted state. The proposed doses are: 5, 30, 60, 180, 240 and 300 mg. The rationale for the starting dose and the planned dose escalation is detailed in Section 8.3. Up to 2 additional dose cohorts can be explored based on the safety, tolerability, and PK of the drug if recommended by the iSRC. The maximum oral dose in Part A will not exceed 480 mg C106.

Subjects will come for 3 visits to the Clinical Research Unit (CRU). Screening (Visit 1) will take place within 4 weeks of the planned dose (Day -28 to Day -1) and will include the subject's signing of the informed consent and an eligibility check, see Table 8.1-1. At Visit 2, subjects will reside at the CRU from Day -1 (the day before IMP administration) until Day 3 for single dose IMP administration, safety, tolerability, and PK assessments as outlined in Table 8.1-1 and detailed in Table 8.1-2. The subjects must fast for at least 10 hours before until 4 hours after the anticipated dosing time on Day 1. During fasting, water, but no other drinks, is allowed as desired. No drinks are allowed for 1 hour before and 1 hour after dosing. The first 2 subjects in each cohort will be dosed in a sentinel fashion, 1 subject will receive C106 and the other will receive placebo as randomised. The subjects will be carefully monitored by clinical staff during and after dosing. Vital signs and ECG will be checked at regular intervals as detailed in Table 8.1-2. Ambulatory ECG telemetry will be used for cardiac surveillance up to 24 hours after IMP administration. There is immediate access to equipment, qualified staff, and an ICU in case of an acute emergency. To give sufficient time for observation of any reactions there will be at least 24 hours before dosing of the remaining 6 subjects, who will be dosed in groups of 3 subjects at least 24 hours apart. A final end-oftrial visit (Visit 3) will take place on Day 7 ( $\pm 2$  days) or after early withdrawal.

Cardiodynamic ECG assessments (collect and store) will be performed in all cohorts (except the first cohort A1) where C106 is given in the fasted state (*i.e.*, not in the fed period of the

fasted/fed cohort) and will include serial ECG extractions at baseline (prior to dosing) and at the same time points as PK sampling during the first 24 hours post-dose.

The doses given after the starting dose and time points for safety and PK sampling may be adjusted as recommended by the iSRC following evaluation of emerging safety, tolerability, and PK data. If needed, one visit for additional safety and PK assessments may be added based on recommendations from the iSRC.

Before initiating a new dose cohort, all subjects in the previous cohort must have been treated and all available safety, tolerability and plasma concentration data up until and including 48 hours post dose must have been evaluated by the iSRC, see Section 8.3.6. After collection of the last available 48-hour data, there will be at least one week between dose escalations. In case of dropouts, available data for the dropouts will be included in the iSRC evaluation. Based on emerging safety and PK data, the amount of required safety and PK data to be reviewed after a completed cohort might be adjusted.

Subjects are expected to participate in Part A for up to 37 days including a 28-day screening period. Subjects who are administered C106 both in the fasted and the fed state in Part A are expected to participate in the trial for up to 43 days + at least 5 half-lives of C106 (wash-out between fasting and fed IMP administrations).

The schedule of events for Part A is shown in Table 8.1-1 and detailed for Visit 2 in Table 8.1-2.

Trial assessments are described in Section 11.

# 8.1.1.1 Food interaction

One dose cohort (planned to be cohort A4) will be selected to investigate any potential food interaction. The predicted maximum exposure (taking into account a possible food interaction effect on the exposure) of the chosen dose level will not exceed the exposure tolerated in previously evaluated cohorts.

Subjects in the selected cohort will return to the clinic after a wash-out period of at least 5 half-lives (as determined by evaluation of PK data) to receive a second dose of C106 or placebo under fed conditions. In case of dropouts at the selected dose level, subjects may be replaced to guarantee a full cohort size for the food-interaction part of the trial (if considered necessary). Any replacers will receive active treatment. The assessments during fed conditions will be the same as during fasting conditions except that the subjects will consume an FDA recommended high-fat, high calorie breakfast 30 minutes prior to IMP administration as detailed in Section 10.5.1 and no screening visit will be conducted. Potential replacement subjects will come for a screening visit and perform one fasting cohort and one fed cohort.

The schedule of events for Part A is shown in Table 8.1-1 and detailed for Visit 2 in Table 8.1-2.

Trial assessments are described in Section 11.

Table 8.1-1 Schedule Visit Assessment	Refer to CTP section:	Screening		nterven rvation		d	Follow-up/End-of-trial		
		Visit 1 Day -28 to Day -1	Visit 2 			Visit 3			
			Admission Day -1	Day 1	Day 2	Day 3	Day 7 (±2) 		
Informed Consent	14.3	Х							
Inclusion/exclusion criteria	9.4, 9.5	Х		Х					
Demographics	11.2	Х							
Medical/surgical history	11.2.5	Х							
HIV, hepatitis B and C	11.2.7	Х							
Alcohol test	11.2.9	Х	Х						
Weight/height (BMI)	11.2.4	Х							
Serum FSH 	11.3.5	Х							
Urine Drug Screen 	11.2.8	Х	Х						
Physical Examination	11.3.2	Х		X 			Х		
Clinical Laboratory Profile 	11.3.5	Х	Х		X	X	Х		
Safety urine sampling	11.3.5	Х	Х		Х	X	Х		
Urinalysis (dipstick)	11.3.5	Х	Х				Х		
Vital Signs 	11.3.4	Х	Х	Х	X	X	Х		
12-lead safety ECG	11.3.2	Х		Х	X	X	Х		
Telemetry	11.3.3			X9					
Randomisation				Х					
IMP administration	10.5			X 					
Cardiodynamic ECG 	11.5.3			Х	X				
PK blood sampling	11.4.1			Х	Х	Х			
PK urine sampling	11.4.2			Х	X	X			
Breakfast					X	Х			
High-fat breakfast 	10.5.1			X 					
Meals 			Х	Х	Х	X			
Adverse events	11.3.1	X							
Prior and concomitant medications	11.2.6	X							

# Table 8.1-1 Schedule of events, Part A (SAD)

BMI=Body mass index. CTP=Clinical trial protocol. ECG=Electrocardiogram. FSH=Follicle stimulating hormone.

HIV=Human immunodeficiency virus.

1. Details in separate flow chart (Table 8.1-2).

2. For the food-effect cohort, each subject will participate in 2 trial intervention and observation periods separated by a washout period.

3. Or after early withdrawal.

4. Females only (questionable cases).

5. Drug tests may also be performed at 1 to 2 additional random occasions during the trial.

6. Symptom driven physical examination.

- 7. Clinical chemistry, haematology and coagulation, see Section 11.3.5.
- 8. Systolic and diastolic blood pressure, pulse, respiratory rate at all visits indicated. Temperature will be measured on Day -1 only (other visits if indicated). For details regarding vital signs, see Section 11.3.4.
- 9. Ambulatory telemetry starting 30 min (±10 min) pre-dose and ending 24 hours (±20 min) post-dose.
- 10. Cardiodynamic ECG (collect and store) from cohort A2 (*i.e.*, not in cohort A1) and not in the fed part in the food effect cohort.
- 11. High-fat breakfast only for subjects participating in the fed part in the food effect cohort, see Section 10.5.1.
- 12. Day -1 Optional evening snack. Day 1: standardised lunch (at least 4 hours post-dose), optional snack, dinner and optional evening snack Day 2: non-standardised breakfast lunch, optional snack, dinner and optional evening snack. Day 3: non-standardised breakfast. For timing of meals, refer to Table 8.1-2.

# Table 8.1-2 Detailed schedule of events, Part A (SAD) Day -1 to Day 2

Tuble 611 2 Dennieu Seneum	Day -1							Day 1							Day 2 Day				
Assessment/time-point (hh:mm)	Admission	Pre- dose	00:00	00:20	00:40	01:00	01:30	02:00	03:00	04:00	06:00	08:00	10:00	16:00	24 h	48 h			
Inclusion/exclusion criteria		X																	
Urine drug screen	Х																		
Alcohol test	Х																		
Physical examination		Х																	
Clinical Laboratory profile	Х														Х	Х			
Safety urine sampling	X														X	X			
Urinalysis (dipstick)	X																		
Vital signs 	X	X			X			X		X	X		X		X	X			
12-lead safety ECG		X			X			X		X	X		X		X	X			
Telemetry 						1			-X						1				
Randomisation		Х																	
IMP administration			X																
Cardiodynamic ECG 									-X										
PK blood sampling		X		X	X	X	X	X	X	X	X	X	X	X	X	X			
PK urine sampling 		X								-X 									
Breakfast 															X	X			
High-fat breakfast 		Х																	
Meals 								X	ζ										
Adverse events								X	ζ										
Prior and concomitant medications								X	ζ										

- 1. Systolic and diastolic blood pressure, pulse, respiratory rate at all time points indicated. Temperature will be measured on Day -1 only (other visits if indicated). For details regarding vital signs, see Section 11.3.4.
- 2. Telemetry: starting 30 min ( $\pm 10$  min) pre-dose and ending 24 hours ( $\pm 20$  min) post-dose.
- 3. A continuous ECG recording will be performed for 25 hours, starting 1 hour pre-dose on Day 1, in all cohorts in which subjects receive C106 or placebo in the fasted state, except for cohort A1. 12-lead ECGs will be extracted at 3 time points within one hour prior to dosing (at -45, -30 and -15 minutes) and subsequently at the same time points as PK blood draws up until and including 24-hours post-dose. Subjects will be supinely resting for at least 15 minutes before and 5 minutes after each time point. When ECG extractions coincide with safety ECGs, vital signs assessment and blood draws, procedures will be carried out in the order outlined in Section 11.1.
- 4. PK urine sampling: pre-dose (blank), 0-6 hours, 6-12 hours, 12-24 hours and 24-48 hours post-dose. No urine sampling in the food interaction cohort.
- 5. Fasting on Day 1. Breakfast on Day 2 and Day 3 after PK blood sampling.
- 6. High-fat breakfast only for subjects in the fed part in the food effect cohort, see Section 10.5.1. Following an overnight fast of at least 10 hours, subjects should start the meal 30 minutes prior to administration of the IMP and eat the meal in 30 minutes or less.
- 7. Day -1: Optional evening snack. Day 1: No breakfast. Standardised lunch at least 4 hours post dose. Standardised snack, dinner and optional evening snack at approximately 7 and 9 and 11 h post-dose. Day 2: Non-standardised breakfast after 24-hour PK sampling, lunch, snack, dinner and evening snack at approximately 4, 7 and 9 and 11 h post breakfast. Day 3: Non-standardised breakfast only.

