# 11.1 Recording of data

The Principal Investigator will provide the Sponsor with all data produced during the trial from the scheduled trial assessments. The PI ensures the accuracy, completeness, legibility, and timeliness of the data reported to Sponsor in the eCRF and in all required reports.

It is important that Cardiodynamic ECG and PK blood sampling occurs as close as possible to scheduled time. In order to achieve this, the timing priority order at a particular time point is:

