#### 11.4 Assessments related to secondary endpoints

#### 11.4.1 *Pharmacokinetic blood sampling and analysis*

Venous blood samples (approximately 5 mL) for the determination of plasma concentrations of C106 after administration of the IMP, will be collected through an indwelling venous catheter at the pre-specified time-points Table 8.1-2 for Part A and Table 8.1-4 and

Table 8.1-5 for Part B). Actual time for blood PK sampling must not deviate more than  $\pm 10\%$  from the planned time except as detailed below.

Pre-dose sampling before the first dose in any Part, may be performed within 60 minutes prior to dosing.

The 24-hour and 48-hour samples in Part A should be taken within  $\pm 2$  hours of the planned sampling time point.

Pre-morning dose sampling on Days 2 to 8 in Part B (MAD) must be performed immediately (within 5 minutes) before dosing.

The date and time of collection of each sample will be recorded in the eCRF.

Samples for determination of plasma concentrations of C106, will be analysed by Lablytica Life Science AB, Uppsala by means of a validated bioanalytical method. The details of the analytical method used will be described in a separate bioanalytical report.

Details on sample collection and handling will be provided in a separate laboratory manual.

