## 11.5.3 Cardiodynamic ECG

Twelve (12)-lead ECGs will be extracted from continuous recordings prior to and serially after dosing at time points presented in the schedule of events for Part A of the trial (Table 8.1-3). Continuous ECG recordings will be performed for 25 hours, starting 1 hour prior to dose administration and baseline ECGs will be extracted at 3 time points before dosing (-45, -30 and -15 minutes). Subjects will be supinely resting for at least 15 minutes prior to each time point for PK sampling.

The 12-lead Holter and ECG equipment will be supplied and supported by Clario. All ECG data will be collected using a Global Instrumentation (Manlius, NY, USA) M12R ECG continuous 12 lead digital recorder. The continuous 12-lead digital ECG data will be stored onto SD memory cards. ECGs to be used in the analyses will be selected by pre-determined time points 5 minutes before each PK sample is drawn as defined in the schedule of events (Table 8.1-3) and may be read centrally by Clario.

If a decision is made to analyse data at the Clario core laboratory, a specific analysis protocol will be developed in accordance with accepted standards for EPQT.

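### The 25-hour Holter recording stops at 24:00 post-dose, but the Part A 24-hour PK sample may be drawn up to 26:00, so the last ECG-concentration pair can be lost or mismatched

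*Combined protocol and SAP*

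**What the plan says.** Four provisions of the protocol meet at the 24-hour time point in the fasted Part A cohorts from A2 onward.

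- **Recording length.** Table 8.1-2 footnote 3: "A continuous ECG recording will be performed for 25 hours, starting 1 hour pre-dose on Day 1". Section 11.5.3 repeats it: "Continuous ECG recordings will be performed for 25 hours, starting 1 hour prior to dose administration". Neither place gives a tolerance for the end of recording.
- **ECG time points.** The same footnote has three pre-dose extractions and then extractions "subsequently at the same time points as PK blood draws up until and including 24-hours post-dose". It adds: "Subjects will be supinely resting for at least 15 minutes before and 5 minutes after each time point".
- **Link between ECG and PK sample.** Section 11.5.3: "ECGs to be used in the analyses will be selected by pre-determined time points 5 minutes before each PK sample is drawn".
- **PK window.** Section 11.4.1: "The 24-hour and 48-hour samples in Part A should be taken within" ±2 hours of the planned time.

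Section 11.1 bears on the same point: "It is important that Cardiodynamic ECG and PK blood sampling occurs as close as possible to scheduled time". It ranks the cardiodynamic ECG and the PK sample first among procedures that fall at the same time.

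**The concern.** The recorder's end time and the PK sampling window were set in different places and do not fit together. Site staff can draw the 24-hour sample late, within the protocol and with no deviation to record, after the Holter has stopped.

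The exploratory objective is to store ECG data for a possible concentration-QTc analysis. Because the data are gathered now for a decision to be taken later, a missing stretch of recording cannot be recovered if that analysis is commissioned. What is at stake is one late, low-concentration pair per affected subject.

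**Working it through.** This is clock arithmetic, with all times relative to dosing.

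**Inputs**
- Recording starts at -1:00 and lasts 25 h (Table 8.1-2 footnote 3; Section 11.5.3).
- The ECG is taken 5 min before the PK draw (Section 11.5.3).
- The 24-hour PK window is ±2 h (Section 11.4.1).
- Post-dose PK times up to 24 h (Table 8.1-2): 0:20, 0:40, 1:00, 1:30, 2:00, 3:00, 4:00, 6:00, 8:00, 10:00, 16:00 and 24:00, which is 12 times.

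**The plan's own figure**
- End of recording = -1 h + 25 h = 24:00. At the nominal draw time the ECG falls at 24:00 - 0:05 = 23:55, inside the recording with 5 min to spare. As scheduled, the plan works.

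**If extraction follows the actual draw**
- Permitted draws: 24:00 ± 2:00 = 22:00 to 26:00.
- Matching ECGs: 21:55 to 25:55.
- Latest draw whose ECG is recorded: 24:00 + 0:05 = 24:05.
- Largest overrun: 25:55 - 24:00 = 1 h 55 min = 115 min.
- Share of the window's width without an ECG: 26:00 - 24:05 = 115 min of 240 min, or 48%. This describes the window only. It is not a probability of loss, and the protocol gives no distribution of draw times from which to obtain one.

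**If extraction follows nominal time**
- The ECG is always at 23:55 and is always recorded.
- A draw at 26:00 comes 26:00 - 23:55 = 2 h 05 min after its ECG. A draw at 22:00 comes 23:55 - 22:00 = 1 h 55 min before it.
- With the interim mean half-life of about 11 h (Section 6.1.7), a 2 h gap corresponds to a factor of 2^(-2/11) = 0.88, a change in concentration of about 12%.

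**Are other pairs affected?**
- The preceding sample is at 16 h with a ±10% window, so at the latest 16 × 1.1 = 17.6 h, well inside the recording. Only 1 of the 12 post-dose pairs is exposed.

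**Recording needed to cover the whole permitted window**
- To the latest ECG: 25:55 + 1:00 = 26 h 55 min.
- To the latest draw plus 5 min of rest: 26:05 + 1:00 = 27 h 05 min, which is 2 h 05 min more than now.

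**Subjects concerned**
- The protocol describes A5 and A6 as still planned: 2 × 8 = 16 subjects, of whom 2 × 6 = 12 receive C106. With the optional A7 and A8 the figures are 32 and 24.

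**The case against.** The strongest reply is that loss needs a late draw. Section 11.1 asks for the ECG and PK sample as near to schedule as possible and ranks them first; subjects are resident; and ±2 h is an outer limit, not the working schedule. This stands as a reason to expect few losses. It does not close the gap, because Section 11.1 neither narrows the window nor tells staff to keep the recorder running until the draw is done. The telemetry footnote in the same table gives its 24-hour end a ±20 min tolerance; the Holter has none.

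Second, Section 11.5.3 speaks of ECGs "selected by pre-determined time points 5 minutes before each PK sample is drawn" and refers to the schedule of events. If that means nominal times, no ECG is lost and a late draw gives only a mismatch. This reading is open, and the text does not choose between the two.

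Third, the consequence is remote. The data are collected and stored, are kept out of the clinical trial report, and would be analysed only under a separate protocol. Peak exposure comes at 20 to 40 minutes. At 180 mg the interim means (Table 8.3-2) bound the 24-hour concentration: with an 11 h half-life the area after 24 h is C24 × 11/ln 2 = C24 × 15.9 h, which cannot exceed 2244 h*ng/mL. So C24 is at most about 141 ng/mL, roughly 5% of the mean Cmax of 2590 ng/mL. This stands, and it keeps the point small.

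Three stronger readings are tempting but not supported:

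- *Late dosing would cost even an on-time draw its ECG.* That assumes a rigid stop 25 h after switch-on. The start is defined relative to dosing, and the same footnote requires extraction through 24 h post-dose; nothing says the device comes off before then.
- *The 24-hour pair is the one that would reveal a delayed effect.* Single 12-lead safety ECGs with QTcF are scheduled at both 24 and 48 hours (Table 8.1-2; Section 11.3.2). They are not Holter extractions, but a late effect would not go unobserved.
- *The rest after the 24:00 time point already overruns the recording.* That rest is a posture rule; the protocol does not say that it must be recorded.

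**Conclusion.** The provisions do not fit together at 24 hours, and the mismatch is worth correcting. On the actual-draw reading, a protocol-compliant draw after 24:05 has no matched ECG, and the ECG time falls up to 115 min after recording ends. On the nominal reading, the ECG at 23:55 can precede its concentration by up to 2 h 05 min.

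The size is small: one of 12 post-dose pairs, exploratory stored data, and no primary or secondary endpoint or stopping rule that uses them. Loss is possible but probably uncommon. That last judgement assumes that most draws cluster near 24:00, as Section 11.1 intends; the documents give no data on it. The finding also assumes that the 25 h and ±2 h figures apply as written in the Holter cohorts. If A5 and A6 are already complete, a change helps only the optional cohorts.

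**What to change.** In Table 8.1-2 footnote 3 and in Section 11.5.3, replace the fixed 25 hours by: *from 1 h pre-dose until the 24-h PK sample and the 5-minute post-sample rest are complete*. Alternatively, keep 25 hours and, in the Holter cohorts only, require the 24-hour PK draw within the recorded time. With the 5-minute offset, a draw after 24:05 cannot have a recorded ECG.

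In either case, state in Section 11.5.3 whether extraction follows the actual or the nominal draw time.

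The first option costs a wording change in two places and at most about 2 hours more recorder wear (2 h 05 min for a draw at 26:00). Subjects stay in the clinic until 48 hours post-dose, so no visit or sample is added. The second option adds no wear but tightens sampling for one time point.
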